Exclusion Criteria: Participants will be excluded if they have an established diagnosis of dementia.

Intervention: The START intervention consists of a Grammatical Reasoning cognitive task delivered online by Wesnes Cognition. This task measures how well the participant can mentally reason the relationships among different shape combinations assigned to grammatical statements. The shapes are a circle and a square, on each trial the square can either be contained within the square, or vice versa. The difficulty of each problem depends on the grammatical statement presented. There are 32 trials in total, 16 being simple questions (e.g. 'the circle is bigger than the square', 'the square contains the circle') and 16 more grammatically complex questions (e.g. 'the circle is not bigger than the square; 'the square does not contain the circle'). Half of each type of trial required the answer YES, and the other

half NO. These responses are made by pressing the left keyboard arrow key for NO and the right keyboard arrow key for YES. Accuracy and speed are recorded for each trial. The task takes around three minutes to complete. Participants will be encouraged to complete the START training once a day for the six-week period of the study

The control group will complete a basic picture-matching task that will provide the same level of engagement, but without the learning effects¹⁰.

Outcome Measures:

The primary outcome measure will be a composite measure of cognitive function, created through a combined score of each of the measures described below, as measured at six weeks. The individual measures will be included as discrete secondary outcome measures. All outcome measures will be completed online. They are sensitive to change in cognition, and validated for use in older adults to detect early changes in cognition.

1. Executive function, as measured by two tests of visual attention and task-switching, the Trailmaking B and the Switching Stroop Test which are validated measures of use in this population.
2. Cognitive function, as measured through the Wesnes Cognition Ltd CogTrack™ system. Individual measures are: Baddeley Logical Reasoning Task (letter sequence)¹¹, Digit Vigilance, Simple and Choice Reaction time, Spatial Working Memory, Numeric Working Memory, Pattern Separation, Word Recall (delayed and immediate) and Word Recognition.

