3. Verbal Learning, as measured through the validated Paired Associate Learning measure, which is highly sensitive to change in cognition and has been used to predict conversion to Alzheimer's Disease in people with cognitive impairment.
4. Activities of Daily Living, as measured by the modified IADL measure which is validated for use in this population, and has been successfully used to show change in IADL in previous online brain training studies.
5. Use of cognitive training: Participants will complete a brief question regarding their use of cognitive training (computer games, crosswords, Sudoku etc) and the regularity of use at each timepoint

Participants will be directed to complete these measures at baseline, two weeks and six weeks, using their 'My Study' homepage on the PROTECT website. Prompts to complete outcome measures will be sent out as automated emails.

Justification for sample size: The sample size calculation is based on the published study of online cognitive training in adults over 50 which showed significant benefit to reasoning, memory and function⁸. Based on an effect size of 0.11, 4826 participants would be required to provide 90% power at a two-sided 0.01 significance level. Assuming a conservative drop-out rate of 50%, a total of 7326 participants will be recruited.

Recruitment and Consent: Recruitment will be achieved through the PROTECT site through promotion of the study to existing participants. Additional publicity will be coordinated to drive recruitment to the PROTECT study overall, with a focus on enrolling new participants into the START trial. This recruitment will be supported by the Royal Devon & Exeter NHS Foundation Trust and the Devon Partnership NHS Trust. This approach has been used to great success during the launch of the previous cognitive training trial, which recruited over 15,000 people over 24 hours. Participants will consent to the study through the established PROTECT online consent process, which enables an electronic records of consent to be taken. Capacity to consent will be monitored as per the approved PROTECT protocol, which involves flagging of significant cognitive decline, an informant questionnaire and regular reminders that people with a diagnosis of dementia are not eligible to continue in the study.

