10. At the end of the study participants will receive a newsletter giving them information on the findings.

Data Analysis

The analysis and presentation of the trial will be in accordance with CONSORT guidelines. Recruitment, intervention uptake, outcome completion rates and drop out will be reported (with 95% CIs) as a flow diagram and the baseline participant characteristics in the intervention and control groups compared.

The primary analysis will undertake an intention to treat between group comparison of primary and secondary outcomes at six months post-randomisation using linear regression adjusting

for baseline outcome value and stratification and minimisation variables. The primary analysis will include complete case data only.

Additional analyses of the primary outcome will take three general forms. First, the influence of missing data will be investigated. As part of our approach to missing data, we will investigate which participant characteristics (including socio-demographic characteristics and baseline clinical values) are associated with primary and secondary outcome scores, and their propensity for missingness. Second, the effect of adherence with intervention will be investigated using allocation respecting methods such as complier averaged causal effects (CACE) modelling using instrumental variable regression. Third, interaction terms will be entered into the primary regression analyses in order to conduct pre-specified subgroup analyses that will include examining impact on groups with early deficits in reasoning, memory and executive function. These will be defined as participants performing outside of one SD of age-matched norms in the reasoning, memory and executive function tasks at baseline. Since the trial is powered to detect overall differences between the groups rather than interactions of this kind, the results of these exploratory analyses will be presented using confidence intervals, as well as a global p-value for the interaction between treatment and each variable, and interpreted with due caution.

No interim analyses are planned. A full analysis plan will be developed prior to completion of data collection and agreed with the Trial Steering Committee and the Data Monitoring and Ethics Committee. All analyses will be undertaken in STATA v.14.

Data Management

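### The primary analysis is called intention to treat but uses complete cases only, with 50% drop-out planned for, no role for the two-week data and no specified re-estimate of the effect under missingness

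*Combined protocol and SAP*

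**What the plan says.** The Data Analysis section describes the primary analysis as an "intention to treat between group comparison of primary and secondary outcomes at six months post-randomisation using linear regression". The covariates are the baseline score and the variables used in allocation. The section then restricts the set: "The primary analysis will include complete case data only".

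The sample size justification reads: "Assuming a conservative drop-out rate of 50%, a total of 7326 participants will be recruited".

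On timing, the Outcome Measures section states: "Participants will be directed to complete these measures at baseline, two weeks and six weeks". The Participant Journey (steps 7 and 9) repeats the two- and six-week assessments and adds one at six months. The Data Analysis section does not mention the two-week data. The primary outcome itself is a composite "created through a combined score of each of the measures described below, as measured at six weeks", which does not agree with the six months in the analysis text.

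On missing data, the Data Analysis section lists its influence as the first of three additional analyses of the primary outcome. The step it describes is that "we will investigate which participant characteristics (including socio-demographic characteristics and baseline clinical values) are associated with primary and secondary outcome scores", and with the propensity for missingness. It names no imputation, weighting, likelihood-based or missing-not-at-random method. A full analysis plan is deferred, to be agreed with the oversight committees before data collection ends.

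**The concern.** An analysis that leaves out everyone without a final outcome is not intention to treat in the usual sense. Under the protocol's own planning assumption it leaves out half of those randomised.

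The baseline-adjusted complete-case regression is unbiased if, given arm, baseline score and the stratification variables, drop-out is unrelated to the outcome. In a remote trial, people may stop because of how they are doing on the tests or the task. The two arms do different tasks, so that dependence may differ between them. A score at two weeks is the best available marker of such a process, and a regression at one later time point cannot use it.

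The stake is high because the target effect is small. At 0.11 SD, a selection effect that would be negligible in many trials could be a sizeable fraction of the effect sought, in either direction. The plan specifies no second estimate of the treatment effect that would reveal this.

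**Working it through.** **1. Inputs from the documents.** Target effect 0.11 SD, 4826 evaluable, 90% power, two-sided 0.01, 50% drop-out (sample size justification). Recruitment is 7239 (Participants) or 7326 (sample size justification). Equal allocation is assumed, as no ratio is stated.

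**2. The plan's own figure.** Total = 4 × (2.576 + 1.282)² / 0.11² ≈ 4920. The stated 4826 is 1.9% lower and is reproduced within rounding of the effect size (an effect of 0.111 gives it).

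**3. Who is analysed.** At 50% loss, 7239 × 0.5 ≈ 3620 complete cases (3663 from 7326). The recruitment totals are a separate matter: 4826 / 0.5 = 9652, whereas 7239 is 4826 × 1.5.

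**4. What bias requires, in general.** Let m be the share lost in an arm and g the completer-minus-dropout gap in the baseline-adjusted outcome, in SD. Then bias = m_START × g_START − m_control × g_control.
- 50% lost in both arms, same gap: bias 0.
- 50% lost in both arms, gap in one arm only: a bias of 0.11 needs g = 0.11 / 0.5 = 0.22 SD.
- Same gap, different rates: 60% versus 40% lost needs g = 0.11 / 0.20 = 0.55 SD; 55% versus 45% needs 1.1 SD.

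**5. A specific mechanism.** These are assumptions, not in the documents: no true effect; 50% retention in each arm; baseline-to-outcome correlation 0.6, so residual SD √(1 − 0.36) = 0.8; partial correlation 0.6 between the two-week score and the outcome; log-odds of retention rising by k per SD of the two-week residual. Let M(k) be the mean standardised two-week residual among those retained. By numerical integration M(0.15) = 0.075, M(0.2) = 0.099, M(0.3) = 0.147 and M(0.5) = 0.236.

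Bias = 0.8 × 0.6 × [M(k_START) − M(k_control)].

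The standard error with 3620 completers is 0.8 × √(4 / 3620) = 0.0266. The false-positive rate at 0.01 is approximately 1 − Φ(2.576 − bias / 0.0266).

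| k in START | k in control | Bias (SD) | False-positive rate |
|---|---|---|---|
| 0.3 | 0.3 | 0 | 1% |
| 0.3 | 0.2 | 0.023 | 4% |
| 0.3 | 0.15 | 0.035 | 10% |
| 0.5 | 0.3 | 0.043 | 17% |
| 0.3 | 0 | 0.070 | 53% |
| 0.5 | 0 | 0.113 | 95% |

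Here k = 0.3 and 0.5 are odds ratios of 1.35 and 1.65 per SD. Simulation agrees, with 0.071 and 0.111 for the last two rows. With a partial correlation of 0.4 instead of 0.6, the 0.3-versus-0 case falls to 0.8 × 0.4 × 0.147 = 0.047.

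**6. Sensitivity to the correlations.** A separate simulated null trial of 7239 used correlations of 0.70 to 0.75, with START retention depending on the two-week score at an odds ratio of 1.65 per SD. It gave a bias of 0.062 SD and 51% rejection at 0.01.

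**7. What the two-week data can repair.**
- Two-week score available for everyone and driving drop-out: the bias falls to about 0.
- Only 60 to 70% complete week 2, and early loss in START follows the same mechanism: 0.071 falls only to 0.04–0.05, and 0.111 to 0.07–0.09. From these rounded figures, between 19% (1 − 0.09/0.111) and 44% (1 − 0.04/0.071) of the bias is removed.
- START drop-out driven by the final score itself (simulation of step 6, odds ratio 1.65): 0.12 falls only to 0.09.

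**The case against.** The strongest reply is that the plan does not ignore missing data. It puts missing data first among the additional analyses of the primary outcome and presents the predictor work as only part of its approach. Finding predictors of outcome and missingness is the usual preparation for imputation or weighting, and a full analysis plan is still to come. All of this stands. A reader might infer that the effect will never be re-estimated; the documents support only that no re-estimate is specified.

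Second, the larger biases need performance-dependent drop-out in START and none in control. The documents give no arm-specific drop-out and no link between drop-out and performance. The control task is meant to engage participants equally, and both arms take the same tests. This also stands. A reader might infer that differential attrition would by itself produce the planned effect. That is arithmetically possible, but only under the harsher one-arm case, and the documents do not show that it is likely. Nor is the 50% a forecast; the protocol calls it conservative.

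Third, baseline-adjusted complete-case regression is valid when missingness depends only on the covariates in the model, so preferring another model is partly a matter of choice. That is true, but the plan gives no reason to expect that condition, and the wider model uses data already scheduled.

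**Conclusion.** The point holds as one about specification. The intention-to-treat label and the complete-case restriction do not fit together. Half of those randomised may be outside the primary analysis, the two-week data are unused, and no re-estimate of the effect under another missing-data assumption is specified. If six months is the intended time point, the six-week data also go unused in the primary model.

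Under the stated assumptions (no true effect, 50% retention, baseline and partial correlations 0.6), the bias runs from about 0, through 0.02–0.05 SD when dependence on two-week performance is unequal between arms, to 0.07–0.11 SD when it is confined to START with log-odds of 0.3–0.5 per SD. The reverse pattern would hide a true effect.

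A reader might also infer that a missing-at-random model cures the problem. It does so only if two-week scores exist for nearly all who drop out and explain the drop-out. With 60–70% completing week 2 it removes less than half in the cases tried, so a departure analysis is needed as well.

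**What to change.** 1. Reconcile the primary time point first: the Outcome Measures section says six weeks and the Data Analysis section says six months.
2. Make the primary analysis one that is valid under missing at random: a repeated-measures mixed model, or multiple imputation by arm, using baseline and all follow-up assessments plus the stratification variables, with the reconciled time point as the primary contrast.
3. Include all randomised participants as far as possible. The Participant Journey randomises (step 4) before the baseline assessment (step 5), so requiring a baseline and a later score would itself select after randomisation. Treat baseline as a response, or impute it where missing, and report how many participants supply no outcome data at all.
4. Keep the complete-case baseline-adjusted regression as a sensitivity analysis and do not call it intention to treat.
5. Add a delta-adjusted (tipping-point) analysis with separate shifts by arm, and report completion at each assessment by arm.

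These changes belong in the full analysis plan that the protocol already promises, with the Data Analysis section amended to match. They need no new data. The cost is wording, some extra Stata code, and slightly more modelling and reporting.
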